3 OBJECTIVES AND ENDPOINTS / OUTCOME MEASURES

3.1 Primary objective

To determine if topical treatment with lidocaine 5% patch (daily administration) or capsaicin 8% patch (periodic administration – upon reoccurrence of pain symptoms) significantly improves health-related quality of life after 6 weeks of treatment compared to systemic (oral) treatment with pregabalin as standard of care in adult patients suffering from localized neuropathic pain across a wide variety of etiologies (LNP), with a duration between 1 and 24 months (subacute to chronic neuropathic pain).

We are interested in 3 comparisons, between on the one hand the systemic versus the topical treatment options (pregabalin versus capsaicin 8% patch, pregabalin versus lidocaine 5% patch), and on the other hand within the topical treatment options (capsaicin 8% patch versus lidocaine 5% patch - as they imply a considerable difference in cost).

3.2 Secondary objectives

- To compare the quality of life profiles over the 24 weeks' treatment period between the treatment arms.
- To compare the effectiveness in terms of pain relief between the treatment arms.
- To compare the effectiveness in different aspects of quality of life (sleep, mood) between the treatment arms.
- To compare the drug tolerance between systemic and topical treatment.
- To identify the difference between topical and systemic treatment in terms of functional status of the patient.

3.3 Endpoints

For details on the primary and secondary endpoints we refer to section 3.4 and 3.5. The EQ-5D-5L was chosen as primary outcome because this is a generic QoL scale recommended by most HTA agencies as this scale can easily be converted to utilities, which is for example not the case with the SF-36. In addition, there exists a validated version in Dutch, French and German. The other option would be to use the SF-36 (v2) questionnaire which has been validated in Dutch and French versions (even specifically for Belgium). However, not much is known about the application of the SF-36 in neuropathic pain conditions as well as during topical treatment conditions (mostly used in mechanical – somatic - pain conditions which are quite distinct from neuropathic pain conditions). In these mechanical pain conditions, a good correlation between SF-36 and the EQ-5D has been shown. For all of the above-mentioned reasons it was decided not to use the SF-36 in this study protocol, but instead use the EQ-5D-5L as the primary endpoint.

All the other measured outcomes are essential to obtain the necessary information regarding the efficacy and tolerability of the therapeutic strategies and their impact on Quality of Life (QoL) and functional status of the treated patients. All proposed

questionnaires are validated and regularly used in the pain setting (belonging in many instances to routine clinical practice).

3.4 Primary endpoint

The primary endpoint is the change in EQ-5D-5L between baseline and week 6.

EQ-5D-5L is a standardized instrument for use as a measure of health outcome, describing states of health in five dimensions: mobility, self-care, usual activities, pain or discomfort and anxiety or depression.

This endpoint is chosen to reflect efficacy (beneficial effect of the compared treatments).

3.5 Secondary endpoints

- Long term quality of life profile;
- Reduction in pain intensity (PI-NRS);
- Time to worsening of the pain and use of rescue medication for pain (MQS III-R);
- Global perceived effect (GPE);
- Effect on mood (Hospital Anxiety and Depression Scale);
- Quality of sleep (NRS and ISI);
- Percentage of patients without systemic drug related side effects (dizziness, fatigue, vertigo, somnolence, headache, blurred vision);
- Time to discontinuation of the study drug and proportion of patients stopping the drug;
- Participation in activities (Utrecht Work Engagement Scale-9);
- Impact of pain on functioning (interference BPI);
- Work Productivity and Activity Impairment (WPAI: Neuropathic Pain, v2.2, Belgium);
- Neuropathic Pain Symptom Inventory (NPSI).

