Currently, the standard approach to all types of neuropathic pain – including the localized neuropathic pain syndromes – is the use of systemic treatment options. However, such systemic treatment often (in a vast majority of patients) leads to systemic side effects such as nausea, vomiting, dizziness, sedation and peripheral edema. These side effects are extremely uncomfortable for the patients and have a high negative impact on their overall quality of life (which is already negatively impacted by the disease state). It is therefore important for patients to avoid the occurrence of systemic side effects. ⁵³ Providing a topical treatment to their localized neuropathic pain syndromes allows patients to avoid systemic side effects, since no systemic absorption occurs during topical administration of analgesic substances. These considerations are especially important since neuropathic pain syndromes are almost always chronic in duration, so long-term (chronic) therapeutic options have to be provided.

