7.7 Trial assessments

The study comprises a screening period of maximum 21 days, randomisation (d-21 to d-1), a baseline visit at day 0 (start of treatment), a treatment period of 24 weeks and a post-treatment period of 2 weeks (24-26 weeks). Considering the pragmatic nature of the proposed trial clinic visits are kept to an absolute minimum.

The **clinical visits** take place at day 0 (V1), week 4 (V2), 12 (V3), 18 (V4), 24 (V5) and 26 (V6) which is comparable to a schedule which would be maintained in routine clinical care. A deviation of +/- 5 days is allowed for the clinical visits. The assessments made at these visits are (*routine care assessments are indicated in bold):*

- Documentation of the study intervention: number of patches (lidocaine and capsaicin), location, dosage used (pregabalin and gabapentin), compliance and discontinuation check
- Documentation of size of painful area
- Assessment of adverse events
- Assessment of systemic drug related side effects (e.g. dizziness, fatigue, vertigo, somnolence, headache, blurred vision) (not on baseline visit)

- · Concomitant medication use
- Only during V2 and V4 clinical sensory testing will be repeated (using the Boston Bedside Quantitative Sensory Testing Battery)

The majority of the assessments (patient reported outcomes and experiences) will be performed by making use of an online platform, enabling patients to complete the different assessments themselves without having to schedule a clinic visit. The use of the online platform will significantly reduce the work load for the patients involved in this study. Per regular weekly online assessment, the required time investment will not exceed 15 minutes. The online assessments on a monthly basis (n = 7 in total) will never require more than 30 minutes (which can be split over different moments).

Online assessments: weekly basis

A deviation of max. 48 hours is allowed for the completion The following procedures and assessments will be carried out:

- Assessment of reduction in pain intensity using PI-NRS
- Assessment of analgesic medication use (using MQS III)
- Quality of sleep: Sleep NRS
- Assessment of systemic drug related side effects (not collected at baseline)
- Discontinuation of study drug (not collected at baseline)
- Participation in activities: Utrecht Work Engagement Scale-9

Online assessments: monthly basis (baseline, week 6, 10, 14, 18, 22)

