7.8 Table of trial procedures

		Treatment Phase					
Visit (V) (°)	Screening (a)	Baseline (V1) ^(b)	V2	V3	V4	V5 (^m)	FU Phase (V6)
Timing of visits (in weeks)	-1	0	4	12	18	24	26
Informed consent	х						
Inclusion/Exclusion criteria	Х						
Demographics (c)	х						
Frequency of alcohol consumption	х						
Medical and surgical history	х						
Pregnancy test	х						
Sensory Testing	х		х		х		
Documentation of study intervention (P)		х	х	х	х	х	
Documentation of size of painful area		х	х	х	х	х	х
Adverse event assessments		х	х	x	х	x	x
Assessments of systemic drug related			х	х	х	х	х
Concomitant medication		x	х	×	×	×	х
Weekly online questionnaire (Appi@Home) (ⁿ) - PI-NRS - MQS-III - Sleep NRS (^f) - Systemic drug related side effects ^(d) - Discontinuation of study drug ^(d) - Utrecht Work Engagement Scale							x
Monthly (e) extended online questionnaire (Appi@Home) - EQ-5D-5L (g) - GPE (d) (h) - HADS (i) - Interference BPI (i) - WPAI (k) - NPSI (i) - ISI (q)		х —					х

(a) Screening is performed d-21 to d-2 prior to the start of the active treatment (b) Randomisation is performed d-21 to d-1 prior to the start of the active treatment (c) Year of birth, age, sex, race, level of education, family situation (d) These variables are not collected at baseline but are included in all other assessments (e) Assessed at baseline, week 6, 10, 14, 18, 22 and 26. Apart from baseline, a deviation of max. +2 days for week 6 and max. +6 days for the other weeks will be allowed for the completion of the different assessments at every time point. Baseline assessment needs to occur one week before V1 and at least 48 hours before V1 (f) Sleep NRS: Sleep Numerical Rating Scale: quality of sleep (g) EQ-5D-5L: Health-related quality of life (h) GPE: Global Perceived Effect (i) HADS: Hospital Anxiety and Depression Scale (j) Interference BPI: Impact of pain on functioning (k) WPAI: Work Productivity and Activity Impairment (I) NPSI: Neuropathic Pain Symptom Inventory (m) Discontinuation of pregabaline needs to be done gradually over a minimum period of 1 week (n) A deviation of max. 48 hours is allowed for the completion of the different assessments at every time point (o) A deviation of +/-5 days is allowed for the clinical visits (p) Number of patches, location, dosage used, compliance and discontinuation check (q) ISI: Insomnia Severity Index Assessments in **bold** are standard of care

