7.11 Withdrawal criteria

A patient has to be withdrawn from active treatment in case any of the following applies:

- The patient requests discontinuation of active treatment;
- The patient is no longer able to participate in the study (e.g. AE, surgery, pregnancy, concomitant diagnoses, concomitant therapies, or administrative reasons). The investigator may also stop a patient's treatment, if the patient is no longer able to attend study visits;
- Significant deviation from the protocol or eligibility criteria. The decision to continue or withdraw treatment will be made after discussion between the sponsor and the investigator at this site;
- The patient cannot tolerate the active treatment:
 - Patients who interrupt or discontinue pregabalin or lidocaine for no more than two weeks or capsaicin for no more than four weeks can continue with their treatment. If the respective treatment interval is longer than described previously, a discussion between the local investigator and the sponsor/Chief Investigator will be necessary and documented in the patient file.
 - A switch between capsaicin and lidocaine or from pregabalin to gabapentin is allowed in case of side effect based on CTCAE v4.03 only if nausea, vomiting, dizziness or decreased level of consciousness grade3 or higher is met. In addition, a switch between capsaicin and lidocaine or from pregabalin

to gabapentin is allowed in case of insufficient pain relief (reduction between 0 – 30%) at maximum dose. If an investigator wants to switch for another side effect than mentioned, the sponsor/Chief Investigator will be contacted by mail and/or phone (if urgent) and the discussion will be made together. A note will be added to the patient file in the medical record (inclusive discussion details like date, participants, side effect and final decision).

• Supportive treatment (standard of care) is allowed at all circumstances at the discretion of the investigator (but no dedicated concomitant medication will be used within the protocol to treat side effects since they are expected to be minimal and of short duration).

Adverse event	Grade 1	Grade 2	Grade 3	Grade 4	Grade 5
Nausea	Loss of appetite without alteration in eating habits.	Oral intake decreased without significant weight loss, dehydration or malnutrition.	Inadequate oral caloric or fluid intake; tube feeding, TPN, or hospitalization indicated.	-	-

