Vomiting	1 – 2 episodes (separated by 5 minutes) in 24 hours.	3 – 5 episodes (separated by 5 minutes) in 24 hours.	>=6 episodes (separated by 5 minutes) in 24 hours; tube feeding, TPN or hospitalization indicated.	Life- threatening consequences; urgent intervention indicated.	Death
Dizziness	Mild unsteadiness or sensation of movement.	Moderate unsteadiness or sensation of movement; limiting instrumental ADL.	Severe unsteadiness or sensation of movement; limiting self care ADL.	-	-
Depressed level of consciousness	Decreased level of alertness.	Sedation; slow response to stimuli; limiting instrumental ADL.	Difficult to arouse.	Life- threatening consequences.	Death.

If cross-over of active treatment (pregabalin to gabapentin, lidocaine to capsaicin or capsaicin to lidocaine) occurs as well as if active treatment is stopped, the corresponding visits will be performed as described in the flow chart. The patient remains in the study and will be followed up as if he/she was still on active treatment.

All withdrawals will be documented and the reason for withdrawal recorded in the patient file (medical record) and in the eCRF and discussed, as necessary, in the clinical trial report.

Patients who fail screening will not be included in the analysis but will be entered into the

trial database (eCRF – OpenClinica). The reason for failure will be documented in the patient file and in the eCRF and reported descriptively and by patient listing in the report of this trial.

Patients who fail screening will be replaced. Patients who initially may not meet eligibility criteria (e.g. for administrative reasons or assessments are out of time window) may be re-screened at investigator's discretion after consulting with the Sponsor (CI). Patients who withdraw from the study after randomisation will not be replaced.

The sponsor reserves the right to discontinue the trial overall or at a particular trial site at any time for the following reasons:

- Emergence of any efficacy/safety information that could significantly affect continuation of the trial;
- Violation of good clinical practice (GCP), the clinical trial protocol (CTP), or the contract by a trial site or investigator, disturbing the appropriate conduct of the trial.

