8.7 Dosage modifications

Dosage of pregabalin is changed every 3 days. Starting dose will be 150mg per day (75mg in the morning and 75mg in the evening). Based on individual response and tolerability, the dose of pregabalin may be further increased to 225mg after an interval of 3 days, and to 300mg after an additional 3-day interval. Dosage can be further increased to the maximum daily dose of 600mg through dosage increases of 75mg every 3 days. Or can be decide otherwise if in accordance with current clinical practice or patient-specific conditions requiring changes to the dosing schedule.

- The dosage of pregabalin can always be modified upon request by the patient. Reasons to modify the dosage could be occurrence of side effects after increase of daily dose (in most cases dizziness, sedation, peripheral edema, blurred vision or nausea and vomiting). In case of side effects, the daily dose should be reduced in first instance by 75mg. If side effects persist additional reductions in daily dose by 75mg should be performed until side effects have (almost) disappeared. All the dose changes (increase and decrease) should be captured in the patient file and the eCRF. If decrease of the dosage appears, also the reason (side effect) will be documented.
- Adjustment of dosage can be done at home following medical guidance.
- Standard of care will be applied to treat side effects.
- Intake of medication can at any time be stopped by the patient if the patient suffers from in his/her opinion unacceptable side effects (no need for tapering down the medication dose).

If systemic treatment is stopped by the patient or the treating physician due to side effects then there is a possibility to switch to another systemic anti-neuropathic treatment, gabapentin. Starting daily dose is 600mg (300mg x 2), to be increased by 300mg every three days to a maximum daily dose of 1800mg (dose including down titration can always be modified by the patient). Or can be decide otherwise if in accordance with current

clinical practice or patient-specific conditions requiring changes to the dosing schedule. Gabapentin is provided by the hospital pharmacy in a dose of 300mg preferably in a package containing 200 capsules. All the dose changes (increase and decrease) should be captured in the patient file and the eCRF. If decrease of the dosage appears, also the reason (side effect) will be documented.

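### The six symptoms that define the systemic side-effect endpoint leave out nausea, vomiting and peripheral oedema, which the protocol elsewhere names as typical systemic or pregabalin effects

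*Protocol*

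**What the plan says.** Section 3.5 of the Protocol gives the secondary tolerance endpoint as the share of patients free of systemic drug-related side effects, followed in brackets by "dizziness, fatigue, vertigo, somnolence, headache, blurred vision", with nothing to mark the symptoms as examples.

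Other sections describe the side effects of systemic treatment differently:

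- Section 2 (Rationale) argues for topical treatment because systemic treatment leads to "systemic side effects such as nausea, vomiting, dizziness, sedation and peripheral edema".
- Section 8.7 gives the side effects that may prompt a change in pregabalin dose as "in most cases dizziness, sedation, peripheral edema, blurred vision or nausea and vomiting".
- Section 7.11 allows a switch of study drug for side effects "only if nausea, vomiting, dizziness or decreased level of consciousness grade3 or higher is met". Any other side effect has to be discussed with the sponsor. After a switch, "The patient remains in the study and will be followed up as if he/she was still on active treatment".

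Section 7.7 repeats the six symptoms for the clinic visits, this time as examples: "Assessment of systemic drug related side effects (e.g. dizziness, fatigue, vertigo, somnolence, headache, blurred vision) (not on baseline visit". The weekly online assessment in section 7.7, the endpoint in the Trial Summary and the analysis text in section 10.3.3 give no list. Note (d) to the table in section 7.8 says of the weekly side-effect item: "These variables are not collected at baseline but are included in all other assessments".

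**The concern.** An endpoint that counts patients free of side effects is only as good as the list of effects it looks for. Here the list omits effects that the protocol itself uses to justify the trial, to guide pregabalin dose reductions and to permit a switch of drug. A patient can therefore have one of the protocol's own reasons for stopping pregabalin and still be recorded as tolerating it without systemic effects.

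The protocol presents these as effects of systemic treatment that topical treatment avoids. On that premise the omission falls mainly on the pregabalin arm and makes it look better tolerated than it is. The comparison at stake is the stated secondary objective of comparing tolerance between systemic and topical treatment.

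The mismatch between sections 3.5 and 7.7 adds a second problem. In a multicentre open-label trial, one site may record only the six symptoms while another records whatever the patient mentions.

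**Working it through.** **Step 1. The lists side by side.** The endpoint list is from section 3.5, the others from sections 2, 8.7 and 7.11.

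| Effect | 3.5 endpoint | 2 Rationale | 8.7 dose change | 7.11 switch |
|---|---|---|---|---|
| Dizziness | yes | yes | yes | yes |
| Blurred vision | yes | – | yes | – |
| Somnolence, sedation or reduced consciousness | yes (somnolence) | yes (sedation) | yes (sedation) | yes (reduced consciousness) |
| Fatigue | yes | – | – | – |
| Vertigo | yes | – | – | – |
| Headache | yes | – | – | – |
| Nausea | **no** | yes | yes | yes |
| Vomiting | **no** | yes | yes | yes |
| Peripheral oedema | **no** | yes | yes | – |

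Of the six effects in section 8.7, two are in the endpoint list by name, one is roughly covered (sedation by somnolence) and three have no counterpart. Of the five in section 2, one is there by name, one is roughly covered and three have no counterpart. Of the four in section 7.11, one is there by name, one is arguably covered and two have no counterpart. Conversely, three of the six endpoint symptoms (fatigue, vertigo, headache) appear in none of the other three lists.

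**Step 2. What follows for one patient.** Take a pregabalin patient who is switched to gabapentin for grade 3 vomiting and reports none of the six listed symptoms. Section 7.11 keeps the patient in follow-up. With the list in section 3.5 read as closed, the patient counts as free of systemic side effects. With the list read as open, as in section 7.7, the patient does not. The result depends on which section is applied.

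**Step 3. The number at risk.** The protocol gives no figure for this endpoint. The only usable one is the arm size in section 10.1, which reproduces: 173 / (1 − 0.12) = 196.6, rounded up to 197 per arm, and 3 × 197 = 591.

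**Step 4. Illustration of size.** Let *f* be the true share of pregabalin patients free of systemic side effects, and *x* the share whose only systemic effects are nausea, vomiting or oedema. With a closed list the counted share is *f* + *x*, so the overstatement is *x*. The protocol gives no value for *x*; the range below is an assumption.

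| Assumed *x* | Patients misclassified, 197 × *x* |
|---|---|
| 2% | 3.9, about 4 |
| 5% | 9.9, about 10 |
| 10% | 19.7, about 20 |

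**The case against.** The strongest reply is that section 3.5 never says its list is exhaustive. The Trial Summary and section 10.3.3 state the endpoint without symptoms, and section 7.7 marks the six as examples. The questionnaire itself is not shown and may have further boxes or a free-text field. This stands to the extent that misclassification is possible, not certain. A reader might infer that a patient switched for vomiting is always a success on this endpoint. The documents do not support that: it needs the closed reading, and the patient must also report none of the six symptoms. The reply does not remove the problem, because section 3.5 is where the endpoint is defined and section 7.7 adds no named symptom.

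A second reply is that such a patient is visible elsewhere: in the discontinuation endpoint, the recorded reason for withdrawal, and adverse event assessment at the visits. That is partly right. But section 9.1 captures only those non-serious reactions that the investigator thinks important. Section 10.3.3 bases the analysis of side effects over time on clinic-visit and self-reported side-effect data and does not mention the adverse event records.

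A third reply is that the protocol's lists also differ among themselves: section 7.11 omits oedema, and section 1 gives yet another list for oral drugs. Section 7.11 also covers the topical drugs and is a switch rule, not an endpoint definition. This is fair, but nausea and vomiting are in all three comparison lists and oedema is in two.

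A reader might also infer that the missing baseline checklist biases the comparison between arms or shrinks the difference by a known fraction. The documents do not support this. The endpoint concerns drug-related effects, randomisation balances existing symptoms in expectation, and no baseline prevalence is given. Existing fatigue, headache or dizziness may add noise, and no more can be said.

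**Conclusion.** The concern holds in a limited form. The endpoint list in section 3.5 does not match the systemic effects named in sections 2, 7.11 and 8.7, and sections 3.5 and 7.7 disagree on whether it is closed. Applied as section 3.5 is written, it can count pregabalin patients with only nausea, vomiting or oedema as free of side effects.

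The likely direction is to understate systemic side effects under pregabalin. This rests on the protocol's own premise that these effects belong to systemic treatment. It is not guaranteed, because patients know their treatment and expectation could raise self-reported symptoms in that arm. An error in the likely direction would work against finding better tolerance with topical treatment.

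The size is unknown. The 4 to 20 patients of 197 follow from an assumed 2% to 10% and show scale only. A reader might want to express the shift in standard errors, but both the share affected and the side-effect-free rates would have to be invented, so the documents support no such statement. One secondary endpoint is affected; the primary analysis and sample size are not.

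**What to change.** Fix one list of systemic side effects that includes nausea, vomiting and peripheral oedema alongside the present six. Use it identically in section 3.5, in the clinic-visit assessment of section 7.7 and in the weekly questionnaire, and state that it is the full list for the endpoint. No change to the dose or switch rules is implied.

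The cost is three extra tick-boxes and no extra visit. The change has to reach the data collection forms, because an analysis plan cannot recover a symptom that was never asked about.

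Optionally, give the same symptom checklist once at baseline, as a reference for symptoms that were already present. This costs one form. It would reduce noise and is not needed to remove a bias between arms.
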